The study will include all patients 19 years or older who are sampled in the NSQIP Hip Fracture Procedure Targeted Dataset from January 2017 through December 2019 and January to December 2021 undergoing surgical fixation of hip fractures using either general and/or spinal anesthesia. In case of reduced Procedure-Targeted data collection during the COVID-19 pandemic, we will also create a total open hip fracture cohort using relevant *Current Procedural Terminology* codes (27244, 27245, 27269, 27236, or 27248) (20).

Exclusion

Patients with the primary or secondary anesthetic technique listed as local anesthesia alone, local anesthesia with intravenous sedation, epidural, and those with no reported anesthesia technique will be excluded. We will further exclude patients with American Society of Anesthesiologists (ASA) Physical Status (PS) V (defined as “5-Moribund”), and patients with ventilator-dependence preoperatively. Patients with platelet counts $< 80,000/\text{mm}^3$ within 90 days before surgery (21), INR ≥ 1.5 , or PTT > 35 seconds were also excluded for the likelihood of these patients being considered ineligible for SA based on previous guidelines (22, 23).

COVID-19 cohorts

The study will be divided into three cohorts: those undergoing hip surgery 1) without COVID-19 infection January to December 2021, 2) with COVID-19 infection January to December 2021, and 3) pre-pandemic from January 2017 to December 2019.

Due to the variable duration of asymptomatic period that can precede symptoms and diagnosis, COVID-19 infection status will be classified as follows. In our primary analysis, COVID-negative patients will be defined as rows 1 in Table 1, and COVID-positive patients will be defined as row 4. In NSQIP, preoperative COVID status denotes within 14 days before surgery, and patients with preoperative COVID are always coded “No” for postoperative COVID. NSQIP does not have previous history of COVID prior to 14 days, which is a major limitation given the increased mortality of patients with recent COVID undergoing surgery (24).

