 1. To assess the association amongst anesthesia type and mortality in COVID-positive patients, a multivariable logistic regression will be performed using a priori exposure (SA vs. GA) and confounder variables (above) for the primary outcome of mortality. The same independent variables will be used in the multivariable logistic regressions for secondary outcomes (linear regression with log transformation for the outcome of length of stay).
4. Sensitivity and exploratory analysis include
 1. We will define the COVID-positive cohort using the additional definitions discussed above per Table 1.
 2. Cohort characteristics of the GA + SA group will be presented, and compared to the SA and GA groups. If this group consists of >1% of the respective cohort, the multivariable logistic regression for mortality will be repeated with GA+SA included as part of the GA group for the multivariable logistic regression.
 3. Repeat the primary modeling with the cohort after excluding patients with age “90” (all patients aged 90 and above are coded as 90+ in NSQIP, thus potential residual confounding)
 4. If there is sufficient sample size, subgroup analysis by sex (male only, female only) and age (<65, >=65 year old) may be performed.
 5. The degree of unmeasured confounding will be assessed using E-value and the Durbin-Wu-Hausman test.
 6. Adjustment for multiple testing for secondary outcomes, including Bonferroni, False Discovery Rate, and Holm's method
5. Sample size calculation
 1. There are approximately 10,000 patients in the NSQIP Hip fracture dataset per year. The prevalence of COVID-19 in the hip fracture patient population was 10% (thus an estimated sample size of approximately 1000 patients) (<https://www.ncbi.nlm.nih.gov/pmc/articles/PMC7495188>), with a mortality

of 36% in this population. The pre-pandemic SA:GA utilization ratio was approximately 1:4 (20). With 80% power and 0.05 alpha, the sample size required to detect a 10% absolute decrease in mortality rate with the SA exposure (from 36% to 26%) is 1064, and 525 for 14% absolute decrease in mortality rate, as calculated by the Sample Size Calculator (<https://clinicalcalc.com/stats/samplesize.aspx>).

2. For population cohort studies where logistic regression is used, the sample size recommended is at least 500 patients, or $100 + 50i$ (i =number of independent variables in the final model) (26). With an estimated sample size of 1000 patients, 18 independent variables can be included.

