3. Sample size calculated based on R-squared (variance explained by the multi-variable logistic regression) and mortality difference between SA vs. GA (Table 2). Assumptions are: alpha = 0.05, baseline mortality rate 36%, ratio of SA:GA of 1:4. For example, with approximately 500-1000 patients from NSQIP, the study would likely be able to detect a 12 to 14% mortality difference depending on the R-squared.

Table 2. Sample size calculation for logistic regression using G*Power software.

Amount of R ² accounted for by covariates	Detectable difference in mortality			
	8%	10%	12%	14%
0.1	1820	1139	771	552
0.2	2048	1281	868	621
0.3	2340	1464	992	709
0.4	2730	1708	1157	827

1.

Data will be analyzed using R. Significance level will be set at P <0.05.

List of variables in cohort characteristics include but are not limited to (Please see Appendix 1 for details)

Patient characteristics: Age, sex, race, body mass index (BMI) (calculated from height and weight in NSQIP), American Society of Anesthesiologists (ASA) Physical Status (PS), smoker within one year preoperatively, severe obstructive chronic pulmonary disease (COPD), dyspnea, coagulopathy, congestive heart failure (CHF), hypertension on medications, preoperative renal failure (acute renal failure, dialysis, and/or GFR < 60 mL/min/1.73 m² based on preoperative creatinine) (25), diabetes, ascites, preoperative functional status, preoperative dementia/delirium, systemic sepsis, preoperative use of mobility aid, and preoperative pressure sore.

Surgical factors: Total operating time, year of surgery, hip fracture type, pathological fracture, and days from hospital admission to operation.

Systems factors: Medical co-management, and participation in a standardized hip fracture care program.

Postoperative variables:

- Mortality
- Myocardial infarction
- Stroke/CVA
- Postoperative delirium
- VTE (composite: pulmonary embolism, DVT)
- Pneumonia
- On ventilator >48h postoperatively
- Acute renal failure
- Sepsis or septic shock (composite of systemic sepsis and septic shock)
- Transfusion (packed red blood cell (PRBC) within the first 72 hours of surgery start time)
- Readmission: also present % unplanned
- Unplanned reoperation
- Still in Hospital > 30 Days
- Non-home discharge
- Weight bearing as tolerated (WBAT) on postoperative day (POD) #1
- Wound issues (composite: superficial and deep infection, wound disruption)
- New postoperative pressure sore
- Urinary tract infection

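### The planned 1000 COVID-positive patients are counted before the row 4 restriction and the exclusions, and the 18-variable allowance holds only at that number and leaves out the exposure

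*Combined protocol and SAP*

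**What the plan says.** Item 1 of the sample size calculation (Statistical Analysis, 5) starts from the whole source: "There are approximately 10,000 patients in the NSQIP Hip fracture dataset per year". It then applies a single factor: "The prevalence of COVID-19 in the hip fracture patient population was 10% (thus an estimated sample size of approximately 1000 patients". Mortality in that population is put at 36%, and the allocation is historical: "The pre-pandemic SA:GA utilization ratio was approximately 1:4". "With 80% power and 0.05 alpha", the item gives 1064 patients for a fall from 36% to 26%, and 525 for a 14-point fall.

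Item 2 takes a published guideline (at least 500 patients, or 100 + 50i, with i the number of independent variables in the final model) and concludes: "With an estimated sample size of 1000 patients, 18 independent variables can be included".

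Item 3 introduces Table 2 and works with roughly 500 to 1000 patients, for which it says a 12 to 14% mortality difference is likely detectable, depending on R-squared.

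The analysed population is set elsewhere. Under COVID-19 cohorts: "COVID-negative patients will be defined as rows 1 in Table 1, and COVID-positive patients will be defined as row 4". Row 4 means laboratory confirmation in the 14 days before surgery; the wider definitions appear only as sensitivity analyses. Under Exclusion, patients with local, sedated-local, epidural or unreported techniques are removed, then: "We will further exclude patients with American Society of Anesthesiologists (ASA) Physical Status (PS) V", along with ventilator-dependent patients and those beyond the platelet, INR or PTT limits. Under Exposure, patients who received both SA and GA leave the primary analysis. The Setting section omits 2020, so COVID-positive patients come from 2021 alone.

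**The concern.** The figure of 1000 has no factor for the COVID definition, the eligibility criteria, the removal of SA+GA patients or deletion for missing data. Each of these can only reduce the number. The size and the variable allowance therefore describe a broader group than the one in which the primary model will be fitted.

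Two things depend on the number. One is how many terms the primary mortality model can carry under the plan's own formula. The other is how a null result will be read: if the protocol says 12 to 14 points was detectable and the achieved cohort could not detect that, absence of a difference will be over-interpreted. The allowance also has a counting problem of its own, because the exposure is an independent variable in the model and is not among the 18 listed confounders.

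**Working it through.** **Inputs from the plan.** 10,000 per year; 10% prevalence; 36% baseline mortality; SA:GA 1:4; 80% power; alpha 0.05 (sidedness not stated; two-sided reproduces the figures); formula 100 + 50i; Table 2.

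**Step 1: reproduce the plan's figures.**
- Size: 10,000 × 0.10 = 1000. No other factor is applied.
- Allowance: (1000 − 100)/50 = 18.
- Required size, two proportions, GA = 4 × SA, no continuity correction: n(SA) = [1.960·√(p̄(1−p̄)(1 + 1/4)) + 0.842·√(p₂(1−p₂) + p₁(1−p₁)/4)]² / (p₁−p₂)², where p₁ is GA mortality, p₂ is SA mortality and p̄ = 0.8p₁ + 0.2p₂.
  - 36% against 26%: p̄ = 0.34, n(SA) = 212.8, total 5 × 212.8 = 1064.
  - 36% against 22%: p̄ = 0.332, n(SA) = 105.0, total 525.

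All four figures reproduce, so the arithmetic is sound. The question is which population it describes.

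**Step 2: count the model terms.** The Confounders section lists 18: age, sex, race, BMI, ASA class, smoking, COPD, dyspnea, coagulopathy, CHF, hypertension, renal failure, diabetes, functional status, delirium or dementia, sepsis, operating time, and days to operation. With SA/GA that is 19, and 100 + 50 × 19 = 1050, which exceeds 1000 before any patient is excluded. Multi-level factors such as race and ASA class add parameters; merging collinear variables or dropping those with much missing data would remove some.

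**Step 3: test the 500 to 1000 range.**
- At 500 the formula allows (500 − 100)/50 = 8 variables.
- At 500 no cell of Table 2 is met; the smallest is 552 (14 points, R² = 0.1). Even without covariate adjustment, the formula in Step 1 gives a detectable difference of 14.3 points at 500.
- At 1000, 14 points is met throughout (largest cell 827), and 12 points is met up to R² = 0.3 (992) but not at 0.4 (1157).

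So 12 to 14% fits the upper end of the range but not the lower end.

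**Step 4: effect of losses.** The documents give no retention figure. The shares below are assumptions for illustration; power and detectable difference are unadjusted, two-sided, at 1:4 with 36% baseline.

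| Share kept (assumed) | N | Variables under 100 + 50i | Detectable difference (points) | Power, 10 points | Power, 14 points |
|---|---|---|---|---|---|
| 100% | 1000 | 18 | 10.3 | 77% | 98% |
| 90% | 900 | 16 | 10.8 | 73% | 96% |
| 80% | 800 | 14 | 11.5 | 68% | 94% |
| 70% | 700 | 12 | 12.2 | 61% | 90% |
| 60% | 600 | 10 | 13.1 | 55% | 85% |
| 50% | 500 | 8 | 14.3 | 47% | 78% |

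Every 50 patients lost costs one variable. A more even split would offset part of this: at an assumed 1:2, the detectable difference at 800 is 9.8 points rather than 11.5. That is possible because MAC is counted as SA and patients likely to be ineligible for SA are removed, but the documents do not give the resulting ratio.

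**Step 5: baseline mortality.** Moribund and ventilator-dependent patients are excluded, so the cohort's mortality may be below 36%. With an assumed 26% falling to 16%, the same formula gives p̄ = 0.24, n(SA) = 167.8 and a total of 839, against 1064. A lower baseline thus needs fewer patients for the same absolute difference. It also yields fewer deaths: at 600 patients, 600 × 0.24 = 144 against 600 × 0.34 = 204.

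**The case against.** The other side has real points, and several limit the claim.

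- **The plan already hedges.** Item 3 works with 500 to 1000 patients, and most plausible losses fall inside that range. This stands as a partial answer. However, 500 is not derived or tied to row 4 or the exclusions, the allowance of 18 is not revised for it, and it does not support the conclusion drawn (Step 3).
- **The rule has two branches.** Item 2 gives a general minimum of 500 as an alternative to 100 + 50i. A reader might infer that the plan's own rule forbids the primary model in a smaller cohort. It does not: a cohort of 500 or more meets the first branch. What fails is the specific statement about 18 variables, which the plan derives from the second branch.
- **Eighteen is a starting list.** Collinearity and missingness may shrink it, so 19 is not necessarily the final count. True, but neither mechanism is tied to the achieved size.
- **The source could grow.** If procedure-targeted collection fell, the Inclusion section allows a wider cohort built from procedure codes. It is tempting to call 1000 a strict ceiling that nothing can offset; this provision rules that out. It is conditional, has no stated size, and is not used in the calculation.
- **The scope of the 10% and 36% is not visible.** The cited source is not among the documents, so it cannot be shown that the 10% spans all COVID-positive rows of Table 1. If it matched row 4 exactly, the 1000 would still precede every eligibility exclusion.
- **It is a fixed registry cohort.** No recruitment target depends on 1000, so the effect is on the model and on interpretation, not on conduct.

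**Conclusion.** The point holds as a mismatch between the population that was sized and the population that will be analysed. On the stated inputs the primary cohort will be smaller than 1000 unless the conditional procedure-code cohort enlarges the source. The 18-variable statement is wrong as written: it holds only at 1000 and omits the exposure, and the starting model of 19 variables needs 1050 under the formula used. The 12 to 14% claim is not supported across 500 to 1000.

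The size of the shortfall is unknown. A reader might go on to infer that the study is underpowered by a definite amount, or that the cohort will be some particular fraction of 1000. The documents support neither: retention, the SA:GA ratio in the eligible cohort and its baseline mortality are all unstated, and the last two could work in the study's favour. The table in Step 4 shows sensitivity to assumed losses; it is not a forecast.

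This should be corrected before analysis. It does not invalidate the design.

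**What to change.** Before mortality is examined:

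1. Count the 2021 row 4 patients who remain after all exclusions and after removing SA+GA patients, by SA and GA, showing the loss at each step. State whether the procedure-code cohort is used.
2. Replace the 1000, the 500 to 1000 and the 1:4 ratio with these counts.
3. Restate the detectable difference and the variable allowance from them, counting the exposure and every model parameter, including those for multi-level factors. Say which branch of the sample size guideline is being applied.
4. If the allowance is below the number of model terms, specify before outcomes are seen how the model will be handled.
5. Show the detectable difference for a baseline below 36% alongside the current one, with the expected number of deaths.

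The cost is one outcome-blind count and a revised sample size section, with no new data. The downside is that the stated size and detectable difference may become less favourable.

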The exposure to either SA or GA will be modelled as a binary variable (please see Appendix 1 for detailed definitions). SA will be defined as having either spinal or managed anesthesia care (MAC) documented the primary anesthesia technique, without GA secondary anesthesia technique. In NSQIP, regional anesthesia with MAC would be coded as MAC for the principal technique. Since it is highly unlikely that patients can tolerate hip fracture repair under sedation alone, MAC is counted as SA for the analysis. Those receiving both SA and GA (presumably either failed spinal and/or conversion to GA for other purposes) will be excluded from the primary analysis, but included in *a priori* sensitivity analysis with cohort characteristics displayed as a third comparison group, and analyzed as part of the GA group for the multivariable logistic regression.

Confounders

We selected an *a priori* list of potential confounders to adjust for the choice of anesthetic technique, based on availability within NSQIP, literature, clinical experience, and consensus within our multidisciplinary team. The confounders are: age, sex, race, body mass index (BMI) (calculated from height and weight in NSQIP), American Society of Anesthesiologists (ASA) Physical Status (PS), smoker within one year preoperatively, severe obstructive chronic pulmonary disease (COPD), dyspnea, coagulopathy (bleeding disorders), congestive heart failure (CHF), hypertension on medications, preoperative renal failure (acute renal failure, dialysis, and/or GFR < 60 mL/min/1.73 m² based on preoperative creatinine) (25), diabetes, preoperative functional status, preoperative delirium or dementia, systemic sepsis, total operating time, and days from hospital admission to operation. The definitions of potential confounding variables collected from NSQIP variables are included in Appendix 1 (Data Extraction Form). Since some of the potential confounders may provide similar information, collinearity will be assessed and variables will be combined or eliminated as described in the statistical analysis plan below.

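### Table 2 does not support detecting a 12–14 point mortality difference with 500 patients, and its R-squared is mislabelled

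*Combined protocol and SAP*

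**What the plan says.** All references are to the combined protocol and SAP, Statistical Analysis, section 5 (Sample size calculation), unless stated.

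- Item 1 gives unadjusted sample sizes at 80% power and alpha 0.05: 1064 for a fall in mortality from 36% to 26%, "and 525 for 14% absolute decrease in mortality rate, as calculated by the Sample Size Calculator". It expects about 1000 COVID-positive patients.
- Item 2 applies the 100 + 50i rule: "With an estimated sample size of 1000 patients, 18 independent variables can be included".
- Item 3 introduces Table 2 thus: "Sample size calculated based on R-squared (variance explained by the multi-variable logistic regression) and mortality difference". It lists its inputs: "Assumptions are: alpha = 0.05, baseline mortality rate 36%, ratio of SA:GA of 1:4". It concludes that "with approximately 500-1000 patients from NSQIP, the study would likely be able to detect a 12 to 14% mortality difference", depending on R².
- Table 2 gives total sample sizes for differences of 8, 10, 12 and 14 points at R² of 0.1, 0.2, 0.3 and 0.4. Its row heading attributes the R² to the covariates but does not say which variable is being explained.

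**The concern.** The concluding sentence of item 3 is the plan's only summary of what the adjusted primary analysis can detect. It gives 500 as the lower cohort size, yet no cell of Table 2 is as low as 500, and item 1 already asks for 525 for 14 points before any adjustment.

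The expected 1000 is 10% of 10,000 patients per year, before the exclusions, so a smaller cohort is a realistic case and the plan names it. If the cohort is near 500, a null mortality result could be read as adequately powered against 12–14 points when it was not.

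The definition of R² matters for the same reason. A reader who picks a Table 2 row from the fit of the mortality model would be using the wrong quantity.

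**Working it through.** **Inputs.** GA mortality 36%, SA:GA 1:4 (SA share B = 0.2) and alpha 0.05 come from item 3. Power of 80% comes from item 1; item 3 does not state it. Sidedness is not stated; two-sided reproduces the table and one-sided does not (1440, 901, 611, 437 at R² = 0.1).

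**Item 1 reproduced.** Pooled two-proportion formula, 14 points, pooled mortality 0.2 × 0.22 + 0.8 × 0.36 = 0.332:

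n(SA) = [1.960 √(0.332 × 0.668 × 1.25) + 0.8416 √(0.22 × 0.78 + 0.36 × 0.64/4)]² / 0.14² = 105.04

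Total = 5 × 105.04 = 525.2. The same formula gives 1064.1 for 10 points. Both agree with the plan.

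**Table 2 reproduced.** Wald test for logistic regression with a binary exposure and the null variance taken at the pooled mortality:

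N = [1.960 √v0 + 0.8416 √v1]² / (log OR)² / (1 − R²)

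For 14 points:
- log OR = logit(0.22) − logit(0.36) = −0.6903
- v0 = 1/(0.2 × 0.8 × 0.332 × 0.668) = 28.18
- v1 = 1/(0.8 × 0.36 × 0.64) + 1/(0.2 × 0.22 × 0.78) = 34.56
- N at R² = 0: (10.405 + 4.948)² / 0.6903² = 494.6
- N at R² = 0.1: 494.6/0.9 = 549.6, against 552 in the table

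Rounded up, the four differences give 1821, 1138, 770, 550 at R² = 0.1 (table 1820, 1139, 771, 552) and 2732, 1707, 1155, 825 at R² = 0.4 (table 2730, 1708, 1157, 827). All 16 cells agree within 2 patients, so the table is sound.

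**Sentence against table.**

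| R² | N for 14 points | N for 12 points |
|---|---|---|
| 0.1 | 552 | 771 |
| 0.2 | 621 | 868 |
| 0.3 | 709 | 992 |
| 0.4 | 827 | 1157 |

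At 500 no cell is met. At 1000 all four 14-point cells and three of the four 12-point cells are met; 12 points at R² = 0.4 is missed.

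**Power at a given N.** Inverting the formula, power = Φ{[|log OR| √(N(1 − R²)) − 1.960 √v0] / √v1}. For N = 500, 14 points and R² = 0.1: (0.6903 × √450 − 10.405)/5.879 = 0.721, so power is 76.5%. Results for R² = 0.1, 0.2, 0.3, 0.4:

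| N | Power, 14 points (%) | Power, 12 points (%) | Detectable at 80% power (points) |
|---|---|---|---|
| 500 | 76.5, 71.9, 66.5, 60.4 | 62.8, 58.1, 53.0, 47.4 | 14.6, 15.4, 16.3, 17.5 |
| 700 | 88.0, 84.3, 79.7, 73.8 | 76.4, 71.7, 66.3, 60.0 | 12.5, 13.2, 14.1, 15.1 |
| 1000 | 96.0, 94.0, 90.9, 86.6 | 88.7, 85.1, 80.4, 74.5 | 10.6, 11.2, 11.9, 12.8 |

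With 500 patients, 80% power for 14 points requires R² ≤ 1 − 494.6/500 = 0.01, below every row of the table. By item 1's formula, 500 patients (100 SA, 400 GA) give 78% without covariates.

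**What R² is.** Multiply each entry by (1 − R²). For 8 points: 1820 × 0.9 = 1638, 2048 × 0.8 = 1638, 2340 × 0.7 = 1638, 2730 × 0.6 = 1638. The other columns are likewise constant, at about 1025, 694 and 496–497. R² therefore enters only as the factor 1/(1 − R²). That is the variance inflation of the exposure coefficient when SA versus GA is itself predictable from the covariates. The share of mortality variance that the model explains is a different quantity.

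**Model size (side point).** (1000 − 100)/50 = 18, so item 2 is exact. The Confounders section lists 18 variables, ending with "preoperative functional status, preoperative delirium or dementia, systemic sepsis, total operating time, and days from hospital admission to operation", and the model adds the exposure: "a multivariable logistic regression will be performed using a priori exposure (SA vs. GA) and confounder variables (above) for the primary outcome of mortality". That is 19 variables, and 100 + 50 × 19 = 1050, before any reduction for collinearity or missing data.

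**The case against.** The sentence is hedged: it is offered as an example, with an approximate cohort size, a likelihood and a dependence on R². It can be read as saying roughly where the 12- and 14-point requirements fall, and seven of those eight cells do lie between 500 and 1000. The plan expects about 1000 patients, where seven of the eight cells are met. The full table is directly below. At 500 patients and R² = 0.1 the shortfall for 14 points is small: 76.5% power, with 14.6 points detectable. The data already exist, so no recruitment decision depends on the sentence. The R² label changes no figure, because the plan commits to no row.

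Much of this stands as to weight: the upper end largely holds, the table is right, and the design is unaffected. The bracket reading does not rescue the sentence, because it states what the study could detect with a given number of patients, and 500 is one of the numbers given. Nor does the hedging cover 47–63% power for 12 points. The row heading does not name the explained variable, so it does not correct the wrong definition in the text.

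The 18-versus-19 point is only a clarification. The rule counts variables in the final model, and one planned removal would bring 19 to 18.

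**Conclusion.** The concern holds. The lower end of the stated range conflicts with Table 2 and with the unadjusted 525 in item 1: at 500 patients, power is below 80% for both 12 and 14 points in every row. The cohort sizes that span 14 down to 12 points are 552–771, 621–868, 709–992 and 827–1157 for the four R² rows. The R² definition is also wrong, as the table's own scaling shows.

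The power and detectable-difference figures assume 36% GA mortality, SA:GA of 1:4, a two-sided 0.05 test and the Table 2 method. The comparison of the sentence with the table needs no assumption beyond the plan's own numbers. This should be fixed, but it does not threaten the design.

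**What to change.** - Replace the concluding sentence of item 3 with, for example: *For R² between 0.1 and 0.4, there is 80% power to detect a difference of about 11–13 percentage points with 1000 patients and about 15–17.5 points with 500.*
- Define R² in item 3 and in the Table 2 heading as the R² from regressing SA versus GA on the confounders.
- For clarity, add 80% power and the two-sided test to the item 3 assumptions.
- For clarity, say in item 2 that the 18 variables include the exposure, so that all 18 confounders plus SA/GA make 19 (1050 patients) before any planned reduction.

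The cost is SAP wording only. The stated detectable difference at the smaller cohort size becomes less favourable. No extra patients are needed, and the endpoint, model, cohort and Table 2 entries do not change.

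### Two recorded care-package variables (standardized hip fracture program, medical co-management) are tabulated but enter no model, so possible confounding of the SA estimate, in either direction, goes unexamined

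*Combined protocol and SAP*

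**What the plan says.** The two variables appear at the end of the Statistical Analysis section, in a list headed "List of variables in cohort characteristics include but are not limited to". The entry reads "Systems factors: Medical co-management, and participation in a standardized hip fracture care program".

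The Confounders section sets an a priori list, chosen "based on availability within NSQIP, literature, clinical experience, and consensus within our multidisciplinary team". It runs from age to "preoperative functional status, preoperative delirium or dementia, systemic sepsis, total operating time, and days from hospital admission to operation". There are 18 entries: 16 patient factors, plus operating time and days from admission to surgery. Neither systems factor is among them, and no reason is given.

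Statistical Analysis item 3 fits the primary model "using a priori exposure (SA vs. GA) and confounder variables (above) for the primary outcome of mortality" and adds: "The same independent variables will be used in the multivariable logistic regressions for secondary outcomes". Item 4 (sensitivity and exploratory analysis) varies the COVID definition, the handling of combined GA and SA, the 90+ age group, subgroups and multiplicity. It also states: "The degree of unmeasured confounding will be assessed using E-value and the Durbin-Wu-Hausman test". Nothing in it adds a systems factor. The Setting section describes multicentre data, and no hospital, site or cluster term is planned.

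**The concern.** An observational comparison of SA with GA depends on its adjustment set, and the Limitations section relies on multivariable adjustment to mitigate confounding by indication. Participation in a care program could plausibly bear on which anesthetic is used and on mortality, delirium, length of stay or discharge home. If so, the adjusted SA estimate would partly reflect the care package.

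The standardized mean differences planned under descriptive statistics could reveal an imbalance between SA and GA patients, but no planned analysis would show what it does to the estimate. The E-value and the Durbin-Wu-Hausman test are directed at unmeasured confounding, whereas these two variables are recorded. If they are added only after an imbalance has been seen, the analysis is post hoc.

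**Working it through.** **1. The plan's own figures reproduce.** Inputs from Statistical Analysis item 5: mortality 36% (GA) against 26% or 22% (SA), SA:GA 1:4, 80% power, alpha 0.05 (taken as two-sided). With pooled p̄ = 0.2·p_SA + 0.8·p_GA,

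n_SA = [1.960·√(p̄(1−p̄)(1+1/4)) + 0.842·√(p_SA(1−p_SA) + p_GA(1−p_GA)/4)]² / (p_GA − p_SA)².

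- 26%: p̄ = 0.340, n_SA = 212.8, total 5 × 212.8 = 1064 (stated: 1064).
- 22%: p̄ = 0.332, n_SA = 105.04, total 525 (stated: 525).
- Variable rule: 100 + 50 × 18 = 1000 (stated: 18 variables at 1000 patients).

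The point therefore concerns the covariate set, not the arithmetic.

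**2. Where each variable is used.**

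| | Descriptive list | Confounder list | Primary and secondary models | Sensitivity analyses |
|---|---|---|---|---|
| Standardized program | yes | no | no | no |
| Medical co-management | yes | no | no | no |
| Days from admission to operation | yes | yes | yes | as in the main model |

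**3. Illustrative size of the bias.** From the documents: overall mortality 36% and SA share 20% (from 1:4). Assumed, because the documents give nothing: program prevalence 30% or 50%; program–SA odds ratio 1.5, 2 or 3; program–mortality odds ratio 0.8, 0.7 or 0.5; no true SA effect. For each combination, solve for the SA share and the mortality with and without the program so that they average 20% and 36%. Then compare crude mortality between SA and GA patients.

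Mid case (prevalence 50%, odds ratios 2 and 0.7):
- SA share is 25.43% with the program and 14.57% without; mortality is 31.90% and 40.10%.
- Program share among SA patients: 0.5 × 0.2543 / 0.20 = 63.6%. Among GA patients: 0.5 × 0.7457 / 0.80 = 46.6%.
- SA mortality: 0.636 × 31.90 + 0.364 × 40.10 = 34.9%. GA mortality: 0.466 × 31.90 + 0.534 × 40.10 = 36.3%.
- False difference 1.4 points, OR 0.94.

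| Scenario | Crude false difference | Crude OR |
|---|---|---|
| Smallest (30%, 1.5, 0.8) | 0.45 points lower with SA | 0.98 |
| Mid (50%, 2, 0.7) | 1.4 points lower with SA | 0.94 |
| Largest (50%, 3, 0.5) | 4.1 points lower with SA | 0.83 |
| Programs go with GA (inverse program–SA odds ratios) | 0.4 to 4.1 points higher with SA | 1.02 to 1.19 |

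These are crude biases. The planned model adjusts for 18 covariates, and the bias remaining after them was not computed.

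**4. Scale.** With 200 SA and 800 GA patients at 36%, the standard error of the difference is √[0.36 × 0.64 × (1/200 + 1/800)] = 3.8 points. The mid case is 1.4/3.8 = 0.37 standard errors; the largest is 4.1/3.8, about 1.1.

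**5. Room in the model.** Counting confounders alone, 19 or 20 variables need 1050 or 1100 patients under the plan's rule, against about 1000 expected. Counting the exposure too, the present set is already 19 variables (1050), and adding both factors makes 21 (1150). Expected deaths are 0.36 × 1000 = 360 with no SA effect, or 0.26 × 200 + 0.36 × 800 = 340 with a 10-point effect. With 21 variables that is 340/21, about 16 deaths per variable.

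**The case against.** The strongest case for the plan has five parts.

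- **The variable limit is already full.** The 18 confounders use the whole allowance at 1000 patients. This stands. A reader might infer that the program variable must go into the primary and every secondary model, but that would exceed the plan's own rule. The rule does not prevent a sensitivity model.
- **Nothing shows that programs go with SA or lower mortality.** This also stands. A reader might infer that the SA benefit will be overstated; the documents do not support a sign, and the same calculation yields false harm if programs go with GA. An unknown sign is still a reason to look.
- **Some background care is already adjusted for, and omitted confounding is addressed.** Admission-to-operation days is partly a care-process measure. The E-value also bears on any covariate left out: for 36% against 26%, RR = 1.385 and the E-value is 1.385 + √(1.385 × 0.385) = 2.11. Both temper the concern. Neither shows what happens when a recorded variable is added.
- **Timing and availability are unknown.** The definitions are in Appendix 1, which is not in the text reviewed. It would be tempting to say that participation is fixed before the anesthetic, or that both variables are already extracted; the text states neither. Co-management may begin after surgery. Both variables might exceed the 10% missing-data threshold or be absent from the cohort built on procedure codes.
- **Other tabulated variables are also unadjusted**, such as hip fracture type, pathological fracture and preoperative mobility aid. This is true, and the documents do not rank them. The systems factors differ in kind: no listed confounder describes the care program or the hospital.

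**Conclusion.** The point holds as a cheap improvement. Two recorded potential confounders are described but never used in any model or sensitivity analysis, with no reason given and no hospital term. The resulting bias could run either way. Under the assumed prevalences and effects it is about 0.4 to 4 points of mortality before adjustment, so within that range it would not by itself produce the 10 to 14 point differences in the sample size text. It could shift an estimate by up to about one standard error. For length of stay, delirium and discharge the size was not calculated. The omission does not invalidate the primary analysis.

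**What to change.** Add to Statistical Analysis item 4 a pre-specified sensitivity analysis that refits the mortality model and the secondary-outcome models in two steps:

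1. with program participation added;
2. with medical co-management also added, reported separately because it may begin after surgery.

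Report the SA odds ratio (for length of stay, the SA coefficient) with and without each addition. State that the existing missing-data rule applies to both variables, and whether they exist in the cohort built on procedure codes. The primary model stays as it is.

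The cost is two extra fits per outcome, with one or two variables beyond the plan's limit of 18 at 1000 patients, in the sensitivity models only. About 340 to 360 deaths are expected on the plan's assumptions. Some precision may be lost: as an illustration, if the covariate R² rose from 0.1 to 0.2, Table 2's sample size for a 10-point difference would go from 1139 to 1281. The actual rise is not known from the documents.
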